10.0 Risk / Benefit Analysis

10.1 Benefits

There are no direct benefits for the subjects participating in this study. However, the knowledge gained from this study may be important for improving short and long - term patient monitoring and providing subjective data, both in the clinic and remotely, for capturing physiological metrics that may aid researchers and healthcare professionals.

10.2 Risks

The risks of the investigational procedure to subjects are expected to be minimal under this protocol and are described in Section 14.5.

The BioStamp nPoint system sensor includes a non-invasive biosensor that is attached to the surface of the skin using an adhesive sticker, and is designed to measure movement, heart rate, heart rate variability, and sleep metrics using embedded accelerometer, gyroscope, and electrodes. The study is designed to assess the system's ability to capture and analyze movement, heart rate, heart rate variability, and sleep.

This is the first clinical trial for this device. The study will enroll healthy subjects at one study site in the United States.

The device will not be used in this study as an implant; it will not be used to support or sustain human life; it will not be of substantial importance in diagnosing, curing, mitigating, or treating disease, or otherwise preventing impairment of human health in this study; and the use in this study will not otherwise present a potential for serious risk to the health, safety, or welfare of a subject. Harm

resulting from use of the device is not considered a serious risk. In addition, no other study procedures will be performed that would place the subjects at significant risk. As indicated in Section 14.5, skin irritation is an anticipated risk.

The BioStamp nPoint system is Non-Significant Risk under the proposed investigational study based on a comprehensive risk analysis per Investigational Device Exemptions, 21 C.F.R. § 812.3(m) (2016) and proposed use of the device¹⁰.

10.3 Minimization of Risk and Monitoring Procedures

MC10 has attempted to mitigate risks as much as possible through product design, testing, and through careful labeling and instructions for use. Risks will be further mitigated through selection of qualified physicians, appropriate training, and study monitoring ensured by the following:

- Investigators who participate in the study will be experienced and skilled in collection of physiological data. Additionally, investigators, in conjunction with the investigational site, will have adequate resources for participation in a clinical study.
- Each investigator will ensure oversight and approval of the study by an Institutional Review Board (IRB) prior to initiation of the clinical study at his/her investigational site.
- The investigator and study personnel will be trained on the clinical protocol, investigational device and Instructions for Use.
- Subjects will be carefully evaluated against the inclusion/exclusion criteria prior to entering the clinical study to ensure that their diagnosis and medical status are appropriate for participation in the clinical study.
- Subjects will be monitored throughout the follow-up period as defined in the study protocol.
- Any adverse events occurring during the time of the investigational procedure will be closely monitored and the subject shall be followed until resolution or is judged to be chronically stable, and any deleterious trends investigated as early as possible.

11.0 STATISTICAL METHODS

11.1 Introduction

The study is a non-significant risk, prospective, non-randomized study of the performance characteristics of the BioStamp nPoint device in healthy adult subjects. Subjects will be enrolled in the trial for approximately 48 hours. The primary objectives of the statistical analyses are to evaluate the agreement of the BioStamp nPoint measurements to commonly accepted measurement standards.

A study center is defined as a hospital or medical office under the control and supervision of the Principal Investigator.

11.2 Sample Size

The sample size of n=25 subjects is sufficient to meet business needs of the Sponsor and is comparable to the size of studies with similar devices. An additional 5 subjects may be enrolled to account for a 20% dropout rate.

11.3 Effectiveness Variables

The effectiveness endpoints for this study are the various types of measurements made by the BioStamp nPoint system. All effectiveness endpoints to be statistically summarized will be collected using the BioStamp nPoint during the supervised-use phase. The effectiveness endpoints are as follows:

- Heart Rate (bpm)
- Heart Rate Variability (RMSSD⁵ (msec) and LF/HF Ratio⁶)
- Respiration (average respiration rate)
- Activity Classification (activities – standing, sitting, lying, walking and other)
- Activity Parameters - total step counts in a 6 minute walk test
- Sleep (sleep onset time (hours, minutes, and seconds), sleep wake time (hours, minutes, and seconds))
- Posture Classification (sleep posture, stationary posture standing, stationary posture sitting)

For each endpoint, the BioStamp nPoint measurements will be compared to a similar FDA approved measurement device, to other basic or manual measurement devices, or to independent observer measurements. The FDA approved measurement devices for this study are the Actiheart heart rate reference device and the Capnostream portable respiratory monitor. Table 10 displays the comparator method for each endpoint category.

Table 10: Endpoint Variable Group and Measurement Comparator

| Index | Endpoint Variable Group | Measurement Comparator |
|-------|-------------------------|-----------------------------|
| 1 | Heart Rate | Actiheart Device |
| 2 | Heart Rate Variability | Actiheart Device |
| 3 | Respiration | Capnostream Device |
| 4 | Activity Classification | Independent Observer |
| 5 | Activity Parameters | Manual Step Counting Device |
| 6 | Sleep Parameters | Independent Observer |
| 7 | Posture | Independent Observer |

Individual independent observers will receive training on the operation of all devices and execution of the study protocol before the enrollment of any subjects.

For heart rate and heart rate variability, the values collected will be the one minute average heart rate, the one minute RMSSD, and the five-minute LF/HF ratio from the BioStamp nPoint and the one minute average heart rate, the one minute RMSSD, and five minute LF/HF from the Actiheart device on each of six recording times for each subject. Two readings will be taken while the subject is at rest, two while exercising and two while lying down. These readings will be collected during the activities listed in Table 7 and Table 8.

For respiration rate, the average resting respiration rate values will be collected at one minute time intervals during sleep on each subject using both the BioStamp nPoint and the Respiration Reference Device.

For the activity classification variable, each subject will be presented with five tasks (standing, sitting, lying, walking and stationary bike riding) in varied order and the activity classification will be recorded by the BioStamp nPoint and by the independent observer. This procedure will be repeated five times for each subject.

⁵ RMSSD: root-mean-square of successive difference of the time intervals between successive heartbeats.

⁶ LF/HF ratio: the ratio of power in the low-frequency (LF, 0.04-0.15 Hz) and high-frequency (HF, 0.15-0.4 Hz) bands of heart rate variability in the frequency domain.

For the exercise parameter “number of steps taken”, the number of steps taken by the subject during a 6 minute walk test will be recorded using both the BioStamp nPoint and a simple step counting device. This procedure will be repeated five times for each subject.

For the sleep parameters sleep onset time and wake time, the BioStamp nPoint values and independent observer values will be collected on each night and morning at the study site.

Posture classification variables will be analyzed separately for each type of posture activity (sleep positions, stationary posture standing and stationary posture sitting). For a given posture activity, the posture classification will be recorded by the BioStamp nPoint and the independent observer for two repeats each of each ground-truth posture for each subject. Each repeat will generate 5 independent observations of posture. The posture classifications for each posture classification variable are given in Table 11.

Table 11: Posture Variable vs Classification

| Index | Posture Variable | Posture Classification |
|-------|-----------------------------|---|
| 1 | Simulated sleep positions | Supine, prone, left side and right side |
| 2 | Stationary Posture Standing | Upright, lean left, lean right, lean back, lean forward |
| 3 | Stationary Posture Sitting | Upright, lean left, lean right, lean back, lean forward |

Sensor adhesion to the subject will be measured on a 4 point scale by the independent observer for each of four sensor patches on each subject following 24 hours of continuous wear. The adhesion rating scale is presented in Table 3.

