8.8.1 Application of the Heart Rate Reference Device

The Heart Rate Reference Device will be applied as described in Section 5.0, following the manufacturer’s IFU, 30 minutes prior to the start of study activities to allow for sensor to body continuity. Heart rate will be monitored throughout the study including during the activities in Table 7 and Table 8.

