8.8.3 Activity Classification

The activities in Table 7 will be conducted as prescribed, in a variable order, and will be annotated by the clinician marking the start and stop times for each activity using the Link App. The particular activity performed for a given annotation will be noted on the CRF. This set of activities will be performed 5 times in a random order each time, as listed in the Repetitions column of Table 7.

Table 7: Activity Classification Activities

| Item | Activity | Description | Time | Repetitions | Metric |
|------|-------------------------|--|-------|-------------|--|
| 1 | Standing Classification | Instruct the subject to stand upright. Once the subject is standing upright, start the activity. | 1 min | 5 | ADL Classifier – Standing HR/HRV – Resting |
| 2 | Sitting Classification | Instruct the subject to sit in a chair. Once the subject is sitting, start the activity. | 1 min | 5 | ADL Classifier – Sitting HR/HRV – Resting |
| 3 | Lying Classification | Instruct the subject to lie supine. Once the subject is lying in a supine position, start the activity. | 1 min | 5 | ADL Lying HR/HRV – Resting |
| 4 | Standing Upright | Instruct the subject to stand against the marked wall, with their right side facing the wall. Instruct the subject to stand upright. Once the subject is in position, start the activity. | 1 min | 5 | Posture HR/HRV – Resting |
| 5 | Standing Leaning FRONT | Instruct the subject to stand against the marked wall, with their right side facing the wall. Instruct the subject to lean forward to the 30-degree mark. Once the subject is in position, start the activity. | 1 min | 5 | Posture HR/HRV – Resting |
| 6 | Standing Leaning BACK | Instruct the subject to stand against the marked wall, with their right side facing the wall. Instruct the subject to lean back to the 30-degree mark. Once the subject is in position, start the activity. | 1 min | 5 | Posture HR/HRV – Resting |
| 7 | Standing Leaning RIGHT | Instruct the subject to stand facing the marked wall. Instruct the subject to lean right to the 30-degree mark. Once the subject is in position, start the activity. | 1 min | 5 | Posture HR/HRV – Resting |
| 8 | Standing Leaning LEFT | Instruct the subject to stand facing the marked wall. Instruct the subject to lean left to the 30-degree mark. Once the subject is in position, start the activity. | 1 min | 5 | Posture HR/HRV – Resting |

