8.8.1 Heart Rate Activities

The activities in Table 8 will be conducted as prescribed and will be annotated by the subject marking the start and stop times for each activity using the Link App. The clinician will train the subject on Link App operation and monitor subject performance to ensure that the activities are properly annotated.

Table 8: Heart Rate Activities

| Item | Activity | Description | Time (minimum) | Repetitions | Metric |
|------|----------|--|----------------|---------------------|------------------|
| 1 | Sitting | Sit comfortably in a chair | 22 min | At least 2, up to 4 | HR/HRV – Resting |
| 2 | Walking | Walk on a treadmill at a comfortable pace | 22 min | At least 2, up to 4 | HR/HRV – Moving |
| 3 | Biking | Bike on a recumbent bike at a comfortable pace | 22 min | At least 2, up to 4 | HR/HRV – Moving |

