12.0 DATA MANAGEMENT

12.1 Data Flow

Data generated by the BioStamp nPoint system and the reference devices, as well as data annotated on the CRFs, will be extracted and time-aligned by MC10 for entry into the trial database. During study execution, ground-truth data collected on CRFs and by reference devices will be stored at the study site. Data collected using BioStamp nPoint will be transmitted to the MC10 Cloud for processing and generation of analytic outputs. The process described below allows verification that the extraction and time-alignment processes do not introduce changes in the underlying data.

After the final subject has completed the study, the sum total of analytic outputs from the study will be exported from the MC10 Cloud and stored in a read-only archive. This archive will be entered into

MC10's Quality system, and a checksum to uniquely represent this archive will be computed. This checksum will be sent for entry into the trial database. After the checksum has been entered, CTI will archive all ground-truth data in a read-only format and compute a checksum on the resulting archive. This checksum will also be entered into the trial database. CTI will then send the ground-truth data archive to MC10 for data extraction and time-alignment. MC10 will then send the relevant data for entry into the trial database and subsequent analysis. All tools to be used in this process will be validated.

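### Heart rate and HRV accuracy is limited to six readings per subject out of at least 287 tagged minutes, with no rule for which minutes, and the five-minute lying LF/HF reading has no activity long enough to supply it

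*Protocol*

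**What the plan says.** Section 11.3 (and Section 4.1 in near-identical terms) defines the paired values as "the one minute average heart rate, the one minute RMSSD, and the five-minute LF/HF ratio from the BioStamp nPoint" and the same quantities from the Actiheart, taken "on each of six recording times for each subject". The split is given as: "Two readings will be taken while the subject is at rest, two while exercising and two while lying down". On their source, Section 11.3 says only: "These readings will be collected during the activities listed in Table 7 and Table 8".

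The activities supply far more than six readings. Under Section 8.8.3, "This set of activities will be performed 5 times in a random order each time", and 19 of the 20 rows of Table 7 carry an HR/HRV tag. All three rows of Table 8 carry it too, each a bout of at least 22 minutes repeated "At least 2, up to 4" times. The section on applying the Heart Rate Reference Device states: "Heart rate will be monitored throughout the study including during the activities in Table 7 and Table 8". Section 6.2 has the chest and thigh sensors configured to compute the algorithm outputs.

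Section 12.1 sets the order of data handling. Device outputs are archived and checksummed, and the ground-truth data are then archived, checksummed and sent to the sponsor for extraction and time-alignment. After that, "MC10 will then send the relevant data for entry into the trial database and subsequent analysis". Section 11.6.2 requires the SAP to be final before database lock.

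**The concern.** Accuracy of the algorithm outputs is part of the primary objective of a study described as pivotal for a 510(k) submission. There are three problems with how these endpoints are fixed.

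- **A restrictive rule is stated.** The number six is written into the endpoint definition, so this is not a detail left open for the SAP. It sets aside most of the paired data, which subjects have already provided.
- **The six are not identified.** No section says which item, which repeat or which minute is the reading, or how the number of Table 8 repetitions is decided. The party that extracts the data holds both signals when it does so.
- **Part of the rule cannot be carried out as written.** LF/HF needs five minutes, and no listed lying activity is that long, so someone has to improvise a window.

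At stake is whether the reported MAE and RMSE describe the device over the tested conditions or over a small, unspecified subset of them.

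**Working it through.** **Stated number of readings.** 2 rest + 2 exercise + 2 lying = 6 per subject. This reproduces the protocol's figure. With 25 subjects: 25 × 6 = 150 heart rate pairs.

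**Tagged minutes per subject (Tables 7 and 8).**

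| Source | Calculation | Minutes |
|---|---|---|
| Table 7 items 1–17 (resting) | 17 × 1 × 5 | 85 |
| Table 7 item 18 (walking) | 6 × 5 | 30 |
| Table 7 item 20 (biking) | 8 × 5 | 40 |
| Table 8, 2 repetitions | 3 × 22 × 2 | 132 |
| **Minimum** | 155 + 132 | **287** |
| With 4 repetitions of Table 8 | 155 + 264 | 419 |

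Item 19 has no HR/HRV tag and is left out. The count takes one run of Table 8. Sections 8.8.10 and 8.9 also place Table 8 activities on Day 1, so 287 is a floor for tagged activity time.

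**Minutes by condition at minimum repetitions.** Lying (items 3 and 14–17): 5 × 5 = 25. Other resting: 12 × 5 + 44 = 104. Moving: 70 + 88 = 158. Sum: 287.

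**Share used.**
- Heart rate and RMSSD (one minute each): 6/287 = 2.1%; 6/419 = 1.4%.
- LF/HF (five minutes each): 30/287 = 10.5%; 30/419 = 7.2%.

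**What that costs in precision.** For n subjects with m readings each and within-subject correlation ρ, the variance of a mean error is proportional to (1 + (m − 1)ρ)/(nm). The ratio of standard errors for m = 6 against m = 287 is √{[(1 + 5ρ)/6] / [(1 + 286ρ)/287]}. The protocol gives no ρ, so a range is assumed:

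| Assumed ρ | SE with 6 readings ÷ SE with 287 |
|---|---|
| 0.05 | 1.98 |
| 0.1 | 1.56 |
| 0.3 | 1.17 |
| 0.5 | 1.08 |

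**Five-minute windows that exist.** Complete non-overlapping windows at minimum repetitions:
- item 18: 5 × 1 = 5
- item 20: 5 × 1 = 5
- Table 8: 3 activities × 2 repetitions × 4 windows = 24

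The total is 34. Of these, 8 are resting (Table 8 sitting, 2 × 4) and 26 are moving. None is lying: every lying item in Table 7 lasts one minute, the items are run in random order, and Table 8 has no lying activity.

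**Order of events.** Reference data reach the sponsor (Section 12.1) before it extracts and forwards what is relevant, a term the section does not define. The SAP deadline is database lock, which can fall after that extraction. Nothing in the protocol requires the windows to be fixed first.

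**The case against.** The strongest reply is that the choice of minute is a derivation rule that belongs in a SAP, and that a few balanced readings per condition is a legitimate design. Part of this stands. An unseen SAP may well fix the windows, and the precision argument is weak if readings within a subject are strongly correlated. It does not dispose of the point: the protocol itself sets the number six, sets a lying LF/HF reading that its own tables cannot supply, and does not require the window rule before the reference data are released.

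Section 12.1 does contain real controls: read-only archives, checksums on both data sets before extraction, and validated tools. They protect the values. They do not govern which windows are forwarded. The complete-case rule in Section 11.7 likewise says which pairs are evaluable, not which are selected.

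A reader might go further in four ways that the document does not support.

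- **That windows will be picked for good agreement.** The protocol leaves this possible; nothing shows it is intended.
- **That repetitions could be added in response to poor agreement.** Heart-rate reference data are downloaded only at the end of wear (Data Download under Section 8.8, and Section 8.11), after the activities. Extra repetitions can only enlarge the pool available later.
- **That the six readings are to be pooled, hiding motion error.** No section says so. Section 11.6.2 computes agreement for each comparison, and the tables tag resting and moving separately.
- **That the possible bias can be bounded.** If errors were independent and normal, keeping the better of 2, 3 or 5 windows would lower expected MAE by 41%, 58% or 73%. That is an illustration only. Correlated windows would give less and larger pools more, and the protocol sets no accuracy threshold for a result to cross.

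**Conclusion.** The point holds in a limited form. The six-reading rule leaves about 98% of tagged minutes unused for heart rate and RMSSD, and about 90% for LF/HF, at minimum repetitions. These shares follow from the protocol's own tables. What they cost in precision is not known: it is substantial if ρ is 0.1 or less and minor at about 0.5 or more. For that reason the open choice of windows matters more than the unused data. That openness is a gap in the protocol, which a SAP could close if it were fixed early enough; it is not evidence of selection.

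The lying LF/HF conflict needs no assumption beyond reading a five-minute value as coming from one continuous activity. Sections 4.1 and 11.3 and Tables 7 and 8 must be reconciled on it. The whole point should be settled before the reference data are released to the sponsor.

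**What to change.** In Section 11.3, with Section 4.1 matched to it:

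1. Replace the six readings by every evaluable paired one-minute window inside the supervised annotated HR/HRV activities for heart rate and RMSSD. For LF/HF, use every complete non-overlapping five-minute window where the activity is long enough (Table 7 walking and biking, and the Table 8 bouts).
2. Report MAE and RMSE separately for resting, moving and lying, with lying for heart rate and RMSSD only. Compute variability with the subject as the cluster.
3. Reconcile the lying LF/HF reading with Tables 7 and 8, or remove it from the endpoint.
4. If six readings are kept, name the item for each condition and fix the windows before ground truth goes to the sponsor. The rule must work for one-minute activities, for example the full annotated minute of the first two repeats. A rule that starts some time after the annotation would leave no complete window in any of the seventeen one-minute HR/HRV rows. Show the all-window result beside the six.

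The cost is more analysis, including a clustered summary, on data already collected. Subjects and site do no extra work.

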For heart rate and heart rate variability, the values collected will be the one minute average heart rate, the one minute RMSSD and the five-minute LF/HF ratio from the BioStamp nPoint and the one minute average heart rate, RMSSD and five minute LF/HF ratio from the Actiheart device on each of six recording times for each subject. Two readings will be taken while the subject is at rest, two while exercising and two while lying down.

For respiration rate, the average sleep respiration rate values will be collected at one minute time intervals during two separate nights of sleep on each subject using both the BioStamp nPoint and the Capnostream while the subject is asleep.

For the activity classification variable, each subject will be presented with five tasks (standing, sitting, lying, walking and stationary bike riding) in varied order and the activity classification will be recorded by the BioStamp nPoint and by the independent observer. This procedure will be repeated five times for each subject.

For the exercise parameter number of steps taken, the number of steps taken by the subject during a 6 minute walk test will be recorded using both the BioStamp nPoint and a simple step counting device.

For the sleep parameters sleep onset time and wake time, the BioStamp nPoint values and independent observer values will be collected on each night at the study site.

Posture classification variables will be analyzed separately for each type of posture activity (sleep positions, stationary posture standing and stationary posture sitting). For a given posture activity, the posture classification will be recorded by the BioStamp nPoint and the independent observer for two repeats each of each ground-truth posture for each subject. Since sleep position and lying posture are identical, this variable will be assessed from awake subjects to ensure that all postures are represented. Each repeat will generate 5 independent observations of posture. The posture classifications for each posture classification variable are given in Table 2.

Table 2: Posture Variable and Classification

| Index | Posture Variable | Posture Classification |
|-------|-----------------------------|---|
| 1 | Sleep positions | Supine, prone, left side and right side |
| 2 | Stationary Posture Standing | Upright, lean left, lean right, lean back, lean forward |
| 3 | Stationary Posture Sitting | Upright, lean left, lean right, lean back, lean forward |

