| 9 | Sitting Upright | Instruct the subject to sit in a straight-backed chair. Instruct the subject to sit upright. Once the subject is in position, start the activity. | 1 min | 5 | Posture HR/HRV – Resting |
| 10 | Sitting Leaning FRONT | Instruct the subject to sit in a chair. Instruct the subject to lean forward to the 30-degree mark. Once the subject is in position, start the activity. | 1 min | 5 | Posture HR/HRV – Resting |
| 11 | Sitting Leaning BACK | Instruct the subject to sit in a chair. Instruct the subject to lean back to the 30-degree mark. Once the subject is in position, start the activity. | 1 min | 5 | Posture HR/HRV – Resting |
| 12 | Sitting Leaning RIGHT | Instruct the subject to sit in a chair. Instruct the subject to lean right to the 30-degree mark. Once the subject is in position, start the activity. | 1 min | 5 | Posture HR/HRV – Resting |
| 13 | Sitting Leaning LEFT | Instruct the subject to sit in a chair. Instruct the subject to lean left to the 30-degree mark. Once the subject is in position, start the activity. | 1 min | 5 | Posture HR/HRV – Resting |
| 14 | Lying SUPINE | Instruct the subject to lie on their back. Once the subject is in position, start the activity. | 1 min | 5 | Sleep posture HR/HRV – Resting |
| 15 | Lying PRONE | Instruct the subject to lie flat on their stomach. Once the subject is in position, start the activity. | 1 min | 5 | Sleep posture HR/HRV – Resting |
| 16 | Lying RIGHT | Instruct the subject to lie on their right side. Once the subject is in position, start the activity. | 1 min | 5 | Sleep posture HR/HRV – Resting |
| 17 | Lying LEFT | Instruct the subject to lie on their left side. Once the subject is in position, start the activity. | 1 min | 5 | Sleep posture HR/HRV – Resting |

| | | | | | |
|----|------------------------|---|-------|---|--|
| 18 | Walking | Instruct the subject to walk for 6 minutes. Once the subject starts walking, start the activity. Count total steps taken by the subject, both legs. Post-activity assessment: How many total steps did the subject take during the walking activity? | 6 min | 5 | ADL Classifier – Walking Pedometer HR/HRV – Moving |
| 19 | Walking Classification | Instruct the subject to walk on the treadmill at a constant, comfortable pace. Once the subject starts walking, start the activity. | 1 min | 5 | ADL Classifier – Walking |

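### Section 11.3 takes two five-minute lying-down LF/HF readings per subject from activity tables whose lying items each last one minute, so the stated source gives four of the six planned readings and none lying

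*Protocol*

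**What the plan says.** Sections 4.1 and 11.3 name heart rate, RMSSD and the LF/HF ratio as effectiveness measures. Heart rate and RMSSD use a one-minute window and LF/HF a five-minute window. Section 11.3 wants all three from the nPoint and from the reference device, including "five minute LF/HF from the Actiheart device on each of six recording times for each subject". Both sections split the six times in the same way: "Two readings will be taken while the subject is at rest, two while exercising and two while lying down". Section 4.1 names no source for the readings. Section 11.3 does: "These readings will be collected during the activities listed in Table 7 and Table 8".

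Table 7 (Section 8.8.3, Activity Classification) has five lying items, numbers 3 and 14 to 17, all tagged for HR/HRV. Item 3 reads "Once the subject is lying in a supine position, start the activity. | 1 min | 5" and item 14 reads "Instruct the subject to lie on their back. Once the subject is in position, start the activity. | 1 min | 5". Items 15, 16 and 17 (prone, right, left) have the same duration and number of repetitions. On order, the section says "This set of activities will be performed 5 times in a random order each time". Table 8 lists sitting, treadmill walking and recumbent biking, each for at least 22 minutes and at least twice. It has no lying activity.

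The section on applying the heart rate reference device adds: "Heart rate will be monitored throughout the study including during the activities in Table 7 and Table 8".

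**The concern.** A five-minute spectral measure cannot be read from a one-minute activity, so the reading count and the source stated in Section 11.3 cannot both hold for LF/HF. LF/HF is a named effectiveness endpoint of a study the synopsis calls pivotal for a 510(k) submission.

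If nothing changes, one of two things happens. The lying LF/HF pairs may be absent, in which case the complete-case rule in Section 11.7 leaves LF/HF agreement resting on rest and exercise alone although the plan promises lying coverage. Or the pairs are taken from a recording outside Tables 7 and 8 that the protocol does not name. Under Section 12.1 the sponsor extracts and time-aligns the data after the nPoint outputs have been exported. The checksums protect the archives, but they do not settle which five minutes are used.

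**Working it through.** **Inputs.** Section 11.3: six recording times (2 rest, 2 exercise, 2 lying), with windows of 1 minute (heart rate, RMSSD) and 5 minutes (LF/HF). Table 7: durations, with 5 repetitions per item. Table 8: minimum 22 minutes, minimum 2 repetitions. Section 11.2: 25 subjects.

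**Formula.** Full windows in a condition = sum over its activities of floor(minutes / window length) × repetitions. Readings obtained = the smaller of that sum and the 2 planned.

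**One-minute measures, lying.** Five items × floor(1/1) × 5 = 25 windows, and 2 are needed. Rest and exercise are amply covered by Table 8 alone. The planned six readings are reproduced for heart rate and RMSSD.

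**Five-minute LF/HF.**

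| Condition | Activities of at least 5 minutes | Windows | Readings |
|---|---|---|---|
| Rest | Table 8 sitting: floor(22/5) = 4, × 2 | 8 | 2 |
| Exercise | Table 8 walking 4 × 2 = 8; Table 8 biking 4 × 2 = 8; Table 7 item 18 floor(6/5) = 1, × 5 = 5; Table 7 item 20 floor(8/5) = 1, × 5 = 5 | 26 | 2 |
| Lying | None: floor(1/5) = 0 for items 3 and 14 to 17 | 0 | 0 |

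Item 18 is the six-minute walk ("6 min | 5 | ADL Classifier – Walking Pedometer HR/HRV – Moving") and item 20 is eight minutes of biking. The total is 2 + 2 + 0 = 4 of 6 readings per subject. At 25 subjects that is 4 × 25 = 100 of 6 × 25 = 150, with 0 of 50 lying. The table counts Table 8 once at its minimum. Sections 8.8.10 and 8.9 schedule its activities again on Day 1, which raises the rest and exercise counts but leaves lying at zero.

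**Could adjacent lying minutes be joined?** If the 20 items of a set are fully randomised, all five lying items fall together with probability 16 / C(20,5) = 16/15504 = 0.10%. A simulation of 300,000 sequences of five sets, allowing runs across set boundaries, gave one run of five lying items in about 1.0% of subjects and two runs in about 0.003%. Such a run always mixes postures. A set has only two supine items (3 and 14), so at most four supine minutes can be adjacent even across a boundary, and the other postures occur once per set. Repositioning would also interrupt the recording.

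**The case against.** The strongest reply is that the data are probably there. Section 5.0 says the Actiheart records inter-beat intervals. Table 5 has it applied on Day 0 and removed on Day 2. Section 6.2 places both nights in the supervised clinic setting, so they fall within the supervised use to which Sections 4.1 and 11.3 confine the endpoints. The nPoint chest sensor is also worn: the first set for at least 24 hours (Section 8.8.7, Sensor Removal), the second until the morning of Day 2 (Section 8.10.3). Most of this stands. What is not explicit is that the nPoint records usable beat data overnight, and Section 11.3 does not point to the night. A reader might infer that lying LF/HF data are lost for good. The documents do not support that; the defect is in the stated source.

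Section 11.3 also does not say that Tables 7 and 8 are the only source. That makes the correction small, but it leaves the lying readings with no named source that can hold them.

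Nor is the Table 7 lying schedule settled elsewhere. Sections 4.1 and 11.3 describe two repeats of each posture with five observations per repeat, against five one-minute repetitions in Table 7. They give no length for a repeat, so they supply no five-minute lying period. The two descriptions should be reconciled at the same time. Table 8 heads its durations as minimums and Table 7 does not, so the one minute is not presented as extendable.

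Finally, the consequence is small. Section 11.6.2 plans plots, MAE and RMSE. The protocol sets no acceptance limit, Section 11.5 plans no subgroup, and no lying-specific result is promised. That stands and limits the weight of the point. Exact window choice may properly sit in the SAP, but a reading count that conflicts with its stated source is in the protocol itself.

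**Conclusion.** The inconsistency is real and confined to LF/HF. Following Section 11.3 as written gives four of six LF/HF readings per subject (100 of 150 at 25 subjects) and none lying. This takes the Table 7 durations at face value and does not join separate lying bouts. LF/HF agreement at rest and during exercise can still be estimated, and one-minute heart rate and RMSSD remain available at all six times.

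A reader might infer that the heart rate variability endpoint as a whole fails, or that the study's conclusions are undermined. Neither follows: one component loses one of three conditions in a descriptive analysis with no pass mark. The point is worth correcting because the plan promises lying coverage that its stated source cannot supply, and because choosing a substitute once the nPoint outputs are in hand would leave avoidable discretion over windows.

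**What to change.** Reconcile Sections 4.1 and 11.3 with Tables 7 and 8 before the nPoint outputs are exported under Section 12.1. Waiting for time-alignment would be too late, because the outputs are already archived by then. Take one of two routes:

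- **(a)** Confirm that both devices hold overnight beat data. Then name the supervised in-bed period as the lying LF/HF source, and state that these windows may include sleep and that posture in bed is not annotated.
- **(b)** Restrict LF/HF to the two rest and two exercise readings, and state that LF/HF agreement was not assessed lying down.

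Under either route, fix every five-minute window in advance by a clock rule, for example the first full five minutes after a set offset in named activities and repetitions. The offset must fit the activity: at most 6 − 5 = 1 minute for item 18, 8 − 5 = 3 minutes for item 20, and 22 − 5 = 17 minutes for Table 8 at its minimum duration. Under (a), the offset could run from the lights-out time on the CRF. Keep one-minute heart rate and RMSSD at all six times.

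The cost is a short written amendment under Section 16.4 and no extra subject time. Route (a) also needs the sponsor's confirmation of the overnight data. Route (b) narrows the LF/HF claim.
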